13.4.4 Tertiary endpoint analysis

For each visit, the percentage of women with a positive result from each IGRA will be estimated with 95% CIs, separately amongst participating women with and without CMV shedding. The distribution of CMV-specific T cell immune responses as measured by each IGRA will also be plotted for each of these groups.

Agreement between the categorical results from the two IGRAs will be assessed using the kappa statistic.

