Criteria for evaluation	
Primary outcome measure(s)
 
 • The prevalence of CMV shedding in saliva, urine and vaginal secretions of CMV seropositive women throughout pregnancy 
Secondary outcome measure(s)
 
 • The quantity of CMV shedding in saliva, urine and vaginal secretions of CMV seropositive women throughout pregnancy • The fold-differences in the prevalence and quantity of CMV shedding in saliva, urine and vaginal secretions in CMV seropositive women throughout pregnancy • The fold-differences in the prevalence and quantity of CMV

	
shedding in saliva, urine and vaginal secretions between different gestational stages of pregnancy in CMV seropositive women
 
 • The risk factors for CMV shedding in CMV seropositive pregnant women • The acceptability of the study procedures to participating pregnant women • The proportion of women approached who are recruited into the study • The proportion of participants completing the study • The relationship between cellular mediated CMV-specific immunity and CMV shedding in CMV seropositive pregnant women
	
Tertiary outcome measure(s)
 
 • The fold-differences in CMV-specific T cell immune responses, as measured by QuantiFERON-CMV and CMV-ELISPOT assays, in the evaluation of CMV-specific T cell responses with CMV shedding in CMV seropositive pregnant women
Sources of funding	Merck Investigator Studies Program
Anticipated start date:	March 2018
Anticipated primary completion date:	April 2021
Sponsor/Co-Sponsor	St George's, University of London
Key Contact names	
Sponsor contact: [name] Email: [contact] [contact]
 
Chief Investigator: [name] Email: [contact] [contact]
 
Principal Investigator: [name] Email: [contact] [contact]

Congenital cytomegalovirus (cCMV)

cCMV is the most common congenital infection in the UK. With an estimated incidence of 3 per 1000 live births (approximately 2400 cases in the UK annually) [Peckham 1983; Griffiths 1991], it is more common than many better known congenital conditions, such as Down's syndrome, spina bifida and cystic fibrosis [Dollard 2007].

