Currently, there are two IFN- γ release assays (IGRAs) which are commercially available to measure CMV-specific T cell immunity; QuantiFERON-CMV assay (manufactured by Cellestis, a QIAGEN Company, Australia), a commercially available enzyme-linked immunosorbent assay (ELISA) to detect IFN- γ released in whole blood by ex-vivo stimulation with human leukocyte antigen (HLA) class I restricted CMV peptides from pp28, pp50, pp65, IE-1, IE-2, and gB; and CMV-ELISPOT, an enzyme-linked immunospot assay which measures IFN- γ production in peripheral blood mononuclear cells (PBMCs) isolated from whole blood following stimulation with CMV antigens pp65 and IE-1. Although both assays measure IFN- γ to detect T cell responses upon stimulation by CMV antigens, their characteristics in terms of methods (ELISA vs. ELISPOT) and principles (CMV-specific CD8+ vs. CD4+ plus CD8+ responses, respectively) are different. In one study, a CMV specific T cell ELISPOT assay was able to predict the risk of CMV viraemia post-transplant in CMV seropositive kidney transplant recipients but a QuantiFERON-CMV assay was not [Lee 2017]. There are no studies which have compared the performance of the 2 assays in the context of CMV shedding in pregnancy.

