The significance of CMV shedding in pregnancy and its relationship with congenital transmission is not well defined. This study aims to lay the groundwork for future studies that will fully assess this relationship.

This study also aims to better characterise the significance of cellular mediated CMV-specific immunity in CMV seropositive pregnant women and its relationship with CMV shedding.

This study will also assess which of the two commercially available IGRAs is best able to measure CMV-specific T cell immune responses in CMV seropositive pregnant women and their association with CMV shedding.

4 Study objectives

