4.3 Tertiary objectives

- To compare the measurement of CMV-specific T cell immune responses between QuantiFERON-CMV and CMV-ELISPOT assays in CMV seropositive pregnant women

5 Trial design

[figure not shown]

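### The rationale promises to say which IGRA is best, but no planned analysis estimates how the two assays differ in their association with shedding

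*Combined protocol and SAP*

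**What the plan says.** The documents describe the purpose of running two assays in three ways.

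- **Section 3.1 (Study rationale)** sets a ranking aim: to "assess which of the two commercially available IGRAs is best able to measure CMV-specific T cell immune responses in CMV seropositive pregnant women". The same sentence extends the aim to how those responses relate to shedding. The background section on cellular immunity leads up to this. It describes a kidney-transplant study in which an ELISPOT assay predicted viraemia and QuantiFERON did not, and adds: "There are no studies which have compared the performance of the 2 assays in the context of CMV shedding in pregnancy".
- **Section 2 (Study synopsis)** gives the tertiary outcome as "The fold-differences in CMV-specific T cell immune responses, as measured by QuantiFERON-CMV and CMV-ELISPOT assays", in relation to shedding.
- **Section 4.3 (Tertiary objectives)** is weaker: "To compare the measurement of CMV-specific T cell immune responses between QuantiFERON-CMV and CMV-ELISPOT assays in CMV seropositive pregnant women". It asks for no winner and does not name shedding.

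Section 14.2.3 defines the tertiary endpoints as detection and quantity of IFN-γ for each assay, at visits with and without shedding.

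Section 13.4.4 then plans three things. First, for each visit, "the percentage of women with a positive result from each IGRA will be estimated with 95% CIs", separately in women with and without shedding. Second, plots of each assay's responses in those groups. Third: "Agreement between the categorical results from the two IGRAs will be assessed using the kappa statistic".

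**The concern.** A claim that one assay is better at tracking shedding needs an estimate of how far the two assays differ in that respect. Section 13.4.4 has none. The percentages and plots treat each assay on its own, and kappa, the only between-assay analysis, takes no account of shedding. High agreement would not show that either assay relates to shedding, and low agreement would not show which one does.

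The mixed model in section 13.4.3 does not fill the gap, because it lists questionnaire risk factors and neither IGRA. The quantity endpoints of section 14.2.3 and the synopsis fold-differences have no estimator at all, only a plot. Any statement about the better assay would therefore have to be read off separate intervals and graphs, with the criterion chosen after the results are seen.

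**Working it through.** The plan gives no figure for the assay comparison, so there is nothing to reproduce. The check is whether any planned quantity changes when the better assay changes.

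**Inputs.** All counts are assumed, because the documents give no IGRA positivity rates and no number of non-shedders to be assayed. I take one result per woman, 60 shedders (30% of 200, the proportion and sample size in section 13.3.1) and 60 tested non-shedders. Rows are QuantiFERON +/−, columns ELISPOT +/−.

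- Shedders: [30, 0; 15, 15]. QuantiFERON positive 30/60 = 50%; ELISPOT positive 45/60 = 75%.
- Non-shedders: [40, 10; 5, 5]. QuantiFERON positive 50/60 = 83%; ELISPOT positive 45/60 = 75%.

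Here only QuantiFERON is associated with shedding.

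**Kappa.** κ = (po − pe)/(1 − pe).

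- Pooled table [70, 10; 20, 20]: po = 90/120 = 0.75; pe = (80×90 + 40×30)/120² = 0.583; κ = 0.167/0.417 = 0.40.
- Assay labels swapped, so that only ELISPOT is associated with shedding: [70, 20; 10, 20]; po and pe are unchanged; κ = 0.40.

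Kappa is the same in two opposite situations. This follows from its symmetry and does not depend on the chosen counts.

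**Dependence on who is tested.** Section 10.6.3 assays the blood of all shedders but only a proportion of never-shedders. In the same illustration κ is (0.75 − 0.50)/0.50 = 0.50 within shedders and (0.75 − 0.667)/0.333 = 0.25 within non-shedders. If all 140 non-shedders were tested in the same proportions, po stays at 0.75, pe becomes 0.617, and pooled κ = 0.133/0.383 = 0.35 instead of 0.40. Pooled kappa thus depends partly on the testing rule.

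**What the planned percentages would show.** QuantiFERON 50% (Wald 95% CI 37 to 63) against 83% (74 to 93); ELISPOT 75% (64 to 86) in both groups. A reader would see the pattern, but the contrast itself is not planned.

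**What a paired contrast adds.** Let D be the QuantiFERON difference (non-shedders minus shedders) minus the same difference for ELISPOT.

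- D = (0.833 − 0.50) − (0.75 − 0.75) = 0.333.
- Each woman has both results, so use her within-woman difference (QuantiFERON minus ELISPOT). In shedders the mean is −15/60 = −0.25 and the variance of the mean is (0.25 − 0.0625)/60 = 0.00313. In non-shedders the mean is 5/60 = 0.083 and the variance of the mean is (0.25 − 0.0069)/60 = 0.00405.
- Half-width = 1.96×√(0.00313 + 0.00405) = 0.166, so the 95% CI is 0.17 to 0.50.
- Treating the four percentages as independent: variance = (0.25 + 0.139 + 0.1875 + 0.1875)/60 = 0.0127; half-width = 1.96×√0.0127 = 0.221.

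Ignoring the pairing would widen the interval by about a third in this example (0.221/0.166 = 1.33). Per-visit numbers would be smaller and the intervals wider.

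**The case against.** The strongest defence is that section 13.4.4 does more than kappa. Percent positive by shedding status, with CIs, is how the plan looks at each assay's relation to shedding, and kappa is there only for agreement. That stands: in the illustration above the percentages do reveal which assay separates the groups. What they lack is an estimate of the between-assay difference, use of the pairing, use of the quantitative results, and a criterion for calling one assay better.

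Three stronger readings are tempting, and the documents do not support them.

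- *The tertiary objective cannot be answered.* Section 4.3 asks only for a comparison of measurement, and kappa with per-assay percentages partly provides one. The unmet aims are those in section 3.1 and the synopsis.
- *The choice of assay for the follow-on study would rest on this.* No section says this study will select an IGRA. Sections 5.2 and 13.2 describe the future work as shedding against congenital CMV, with shedding prevalence as a key input to its size.
- *Positive/negative calls are uninformative because every participant is seropositive.* Sections 10.6.3.1 and 10.6.3.2 say the assays monitor cell-mediated immunity and are not tests for infection, so serostatus does not fix the result.

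It is also fair to say that this is a tertiary aim in a feasibility study, for which description alone would be a legitimate choice. In that case the rationale should not promise a ranking.

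**Conclusion.** The concern holds as a mismatch between a stated aim and its analysis. Section 3.1 promises to identify the better assay, including for association with shedding, and the synopsis promises fold-differences. Section 13.4.4 supplies an informal side-by-side description and an agreement statistic that cannot rank the assays. That kappa is symmetric and ignores shedding is a matter of algebra and needs no assumption. The values 0.40, 0.35 and 0.33 rest on assumed counts and only illustrate the point. No figure for this trial can be derived, because positivity rates and the number of never-shedders tested are not given. The effect is confined to the tertiary assay comparison; no primary or secondary estimate changes. It is worth correcting because the remedy uses results the study will already have.

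**What to change.** In section 13.4.4, keep kappa and the percentages as description, and add the following, settled before any IGRA results are seen.

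1. On blood samples with both assay results, estimate each assay's association with shedding from its quantitative result, for example as an AUC, which suits assays on different scales.
2. Name the ELISPOT summary in advance. Section 10.6.3.2 yields spot counts from separate IE-1 and pp65 panels, whereas section 14.2.3 expresses the ELISPOT endpoint in IU/ml in plasma.
3. Report the paired difference between assays with a 95% CI from a bootstrap that resamples women, so that repeat visits stay together. Base any statement about the better assay on that difference.
4. State whether estimates are conditional on, or weighted for, the selection of never-shedders described in section 10.6.3.

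If no ranking is wanted, reword section 3.1 to agreement and description, and reconcile the fold-difference outcome in the synopsis with it.

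The cost is some SAP text and a modest analysis, with no new samples or visits. The drawback is that with few shedders the interval will be wide and may not identify a better assay; the report should then say so.

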13.4.5 Sensitivity and other planned analyses (if applicable)

A subgroup analysis will be performed using data only from women with samples at all three time points.

13.5 Interim analysis

There will be no need for interim analyses to be performed.

14 Committees involved in the trial

This study will have a Trial Management Group. This group will include those individuals responsible for the day-to-day management of the study, including the CI, the PI, senior investigators at the site, the study midwife involved in the study, the virologist coordinating the laboratory analysis of the samples, the project manager and the statistician. The role of the group is to monitor all aspects of the conduct and progress of the trial, ensure that the protocol is adhered to and take appropriate action to safeguard participants and ensure the quality of the trial.

15 Direct access to source data

The Investigator(s)/institution(s) will permit trial-related monitoring, audits, REC review, and regulatory inspection(s), providing direct access to source data/documents. Trial participants are informed of this during the informed consent discussion. Participants will consent to provide access to their medical notes.

16 Ethics and Research Governance requirements

Before the site can enrol patients into the trial, the Chief Investigator must ensure written permission to proceed has been granted by their Research & Development (R&D) department. At St George's the governance team within the JRES can provide assistance.

The site must conduct the trial in compliance with the protocol as agreed by the Sponsor and which was given favourable opinion by the Research Ethics Committee (REC).

The Chief Investigator will be provided (via the Sponsor) with file indexes E.G. JRESDOC0003 TMF index and JRESDOC0004 ISF index for use with SOP JRESSOP0019 'Preparation and Maintenance of the TMF' The CI will be responsible for the maintenance of the TMF and may delegate the responsibility of ISF file maintenance.

It is the responsibility of the Chief Investigator to ensure that all subsequent amendments gain the necessary approval. Refer to JRESSOP0011 'Management of Amendments'.

Within 90 days after the end of the trial, the CI and Sponsor will ensure that the REC is notified that the trial has finished. If the trial is terminated prematurely, those reports will be made within 15 days after the end of the trial. Refer to JRESSOP0015 'End of study declaration'

The CI will supply an End of Study report of the clinical trial to the REC within one year after the end of the trial. The sponsor can provide JRESDOC0059 End of study Report template

17.1 Annual Progress Reports (APRs)

The Chief Investigator will prepare the APR in accordance with JRESSOP0043. Following review by the sponsor the report will be sent to the REC. The APR is due for submission annually within 30 days of the anniversary date on which the Ethics committee gave the favourable opinion, until the trial is declared ended.

17.2 Notification of Serious Breaches of GCP and/or the protocol

Any Protocol Deviations or violations will be documented using JRESDOC0061, and entered onto the Sponsor's log JRESLOG0005. Potential Serious Breaches and Urgent Safety Measures will be recorded both on the Sponsor's Log JRESLOG0005 and processed according to JRESSOP0012 and where necessary JRESSOP0032

A "serious breach" is a breach that is likely to effect to a significant degree:

- (a) The safety or physical or mental integrity of the participants of the trial; or
- (b) The scientific value of the trial.

The CI will notify the Sponsor immediately of any case where there exists a possible occurrence of a serious breach.

17 Finance

This study is funded by the Merck Investigator Studies Program (MISP No. 58414).

18 Insurance and indemnity

St George's, University of London holds insurance to cover participants for injury caused by their participation in the clinical trial. Participants may be able to claim compensation if they can prove that St George's, University of London has been negligent. This includes negligence in the writing of the protocol, or selection of trial resources.

Where the Trial is conducted in a hospital, the hospital has a duty of care to participants. St George's, University of London will not accept liability for any breach in the hospital's duty of care, or any negligence on the part of hospital employees. Hospitals selected to participate in this clinical trial shall provide clinical negligence insurance cover for harm caused by their employees and a copy of the relevant insurance policy or summary shall be provided to St George's, University of London, upon request.

Participants may be able to claim compensation for injury caused by participation in this Trial without the need to prove negligence on the part of St George's, University of London or another party.

If a participant indicates that they wish to make a claim for compensation, this needs to be brought to the attention of St George's, University of London immediately.

Failure to alert St George's, University of London without delay and to comply with requests for information by the sponsor or any designated Agents may lead to a lack of insurance cover for the incident.

19 IP and development policy

Unless otherwise specified in agreements, the following guidelines shall apply: All Intellectual Property Rights and Know How (IP) related to the Protocol and the Trial are and shall remain the property of the Sponsor excluding

- 1) Pre-existing IP related to clinical procedures of any Hospital.
- 2) Pre-existing IP related to analytical procedures of any external laboratory.

All contributors shall assign their rights in relation to all Intellectual Property Rights and in all Know How, not excluded above to the Sponsor and at the request and expense of the Sponsor, shall execute all such documents and do all such other acts as the Sponsor may reasonably require in order to vest fully and effectively all such Intellectual Property Rights and Know How in the Sponsor or its nominee. They shall promptly disclose to the Sponsor any Know How generated pursuant to this Protocol and not excluded above and undertake to treat such Know How as confidential information jointly owned between it and the Sponsor.

Nothing in this section shall be construed so as to prevent or hinder any medical professional from using Know How gained during the performance of the Trial in the furtherance of its normal business

activities, to the extent such use does not result in the disclosure or misuse of Confidential Information or the infringement of any Intellectual Property Right of the Sponsor.

20 Publication policy

Publication: "Any activity that discloses, outside of the circle of trial investigators, any final or interim data or results of the Trial, or any details of the Trial methodology that have not been made public by the Sponsor including, for example, presentations at symposia, national or regional professional meetings, publications in journals, theses or dissertations."

All scientific contributors to the Trial have a responsibility to ensure that results of scientific interest arising from Trial are appropriately published and disseminated. The Sponsor has a firm commitment to publish the results of the Trial in a transparent and unbiased manner without consideration for commercial objectives.

To maximise the impact and scientific validity of the Trial, data shall be consolidated over the duration of the trial, reviewed internally among all investigators and not be submitted for publication prematurely. Lead in any publications arising from the Trial shall lie with the Sponsor in the first instance.

20.1 Before the official completion of the Trial

If an investigator wishes to publish a sub-set of data before completion of the trial, the Chief Investigator must be consulted.

20.2 Up to 180 days after the official completion of the Trial

During this period the Chief Investigator shall liaise with all investigators and strive to consolidate data and results and submit a manuscript for peer-review with a view to publication in a reputable academic journal or similar outlet as the Main Publication.

- The Chief Investigator shall be senior and corresponding author of the Main Publication.
- Other investigators shall be listed as compatible with the policies of the publication outlet and good academic practice.
- Providers of analytical or technical services shall be acknowledged, but will only be listed as co-authors if their services were provided in a non-routine manner as part of a scientific collaboration.

Appendix 1 Summary of Protocol Revision History

Appendix 1

There are currently no amendments to the protocol.

Protocol amendment /Revision History

Protocol Version and Date	New text
2.0 08/08/19	Details on screening process has been updated throughout the study protocol to reflect changes required for the study screening period to extend to 12 months. The range of gestational ages to reflect the appropriate corresponding trimesters were also corrected.
3.0, 25/03/20	Addition of section 10.6.5. Sample collection and sample storage due to disruption caused by COVID-19 Pandemic
